9 RISKS AND DISCOMFORTS

9.1 BCG Vaccine Risks

The BCG injection is associated with minimal, brief discomfort. The following risks may also be associated with BCG vaccination per the manufacturer product insert.

Although BCG vaccination often causes local reactions, serious or long-term complications are rare. Reactions that can be expected after vaccination include moderate axillary or cervical lymphadenopathy and induration and subsequent pustule formation at the injection site; these reactions can persist for as long as 3 months after vaccination. The intensity and duration of the local reaction depends on the depth of penetration of the puncture device and individual variations in patients' tissue reactions. Slight tenderness at the puncture site may be encountered as well as some itching. The initial skin lesions usually appear within 10–14 days and consist of small red papules at the site. The papules reach maximum diameter (about 3 mm) after 4 to 6 weeks, after which they may scale and then slowly subside. More serious local reactions include ulceration at the vaccination site, regional suppurative lymphadenitis with draining sinuses, and caseous lesions or purulent draining at the puncture site. These manifestations might occur up to 5 months after vaccination and could persist for several weeks.

Acute, localized irritative toxicities of BCG may be accompanied by systemic manifestations, consistent with a “flu-like” syndrome. Systemic adverse effects of 1–2 days’ duration such as fever, anorexia, myalgia, and neuralgia, often reflect hypersensitivity reactions. However, symptoms such as fever of 103 °F or greater, or acute localized inflammation persisting longer than 2–3 days suggest active infections, and evaluation for serious infectious complication should be considered.

Rare adverse events (mostly suppurative adenopathy) have been reported in Europe and other locales, mostly in the setting of mistakenly subcutaneous, rather than intradermal vaccination. The frequency of more severe cutaneous reactions, such as an ulcer >1 cm, axillary adenopathy which may be suppurative, or other localized skin reactions, is approximately 0.02% for first vaccinations and 0.04% for second vaccinations. Suppurative adenopathy is not treated but observed.

The most serious complication of BCG vaccination is disseminated BCG infection. The most frequent disseminated infection is BCG osteomyelitis (0.01 to 43 cases per million doses of vaccine administered) which usually occurs 4 months to 2 years after vaccination. Fatal disseminated BCG infection has occurred at a rate of 0.06–1.56 cases per million doses; these deaths occurred primarily among immunocompromised persons (tested for and excluded from this study).

9.2 Lumbar puncture

Pain may occur during the procedure. This is usually temporary, confined to the lower back, and minimized with the cutaneous and soft tissue administration of 1% lidocaine as a local anesthetic. Short-lived LP associated headaches occur in <1%–36% of subjects with an incidence that decreases with age. Less commonly, a persistent low-pressure headache may develop as a result of a post-LP CSF leakage. Potentially more serious, but very rare risks, include infection, damage to radicular nerves and bleeding into the lumbar CSF space. The risk of these procedure related complications is much less than 1%. There is also a very rare risk of an allergic reaction to the lidocaine.

9.3 Magnetic Resonance Imaging (MRI)

MRI is a safe procedure for participants who do not have metal implants or other contraindications. Individuals who have electrically, magnetically, or mechanically-activated implants (such as heart pacemakers) or those who have clips on blood vessels in their brain will not be allowed to participate in the study due to risks associated with MRI scanning. The MRI will be operated in a manner accepted by the Food and Drug Administration (FDA). The protocol requires participants to remain still within a relatively confined space during the scanning session, and the scanner makes loud knocking and beeping sounds as it takes images. While participants with severe claustrophobia are excluded from the study, some participants may find the physical confinement or noise uncomfortable. Every effort will be made to enhance each subject’s comfort level, and participants will be given earplugs to reduce discomfort due to noise. If a subject notices any discomfort while in the MRI scanner, they should notify the administrator immediately. If the discomfort cannot be stopped, the scanning session will be stopped. The MRI has the potential, during normal routine use, to cause localized warming of the skin and underlying tissues. Participants should immediately inform the study staff if they experience discomfort due to warming of the skin and the procedure will be stopped.

9.4 Phlebotomy

The risks associated with having blood drawn include bruising and local discomfort. Rarely an infection may occur at this site, and if an infection does occur it will be assessed and treated by the study physician.

9.5 Neurocognitive testing

The neurocognitive tests that will be administered to assess mental performance may be stressful and potentially cause anxiety, fatigue, and frustration. In our prior experience with similar protocols, risks have occurred infrequently and very few subjects have terminated testing. However, testing will be discontinued immediately upon any request by the subject to do so.

9.6 Neuropsychiatric and Functional Questionnaires

Questionnaires administered during the protocol may cause participants to feel sad or upset about their diagnosis and daily functioning or how it affects their quality of life. Study staff is experienced with such evaluations and sensitive to these issues. Any question can be omitted per the subject's request.

9.7 Radiation

In general, exposure to ionizing radiation may have health risks. Participants who require fluoroscopy-guided LP will be exposed to a maximum of approximately 0.18 millisieverts (mSv) for each LP. This is the same amount of radiation as a person would normally get in 21 days from natural background radiation and is comparable to the dose from a single chest x-ray.

9.8 Genetic Research Risks

The study includes the potential to generate genetic data from patient samples. Genetic information that results from this study does not have medical or treatment importance at this time. Genetic information obtained in this study will not be placed in the medical record. Taking part in a genetic study may also have a negative impact on family or other relationships. We will inform subjects that there may be new technologies that may be developed in the future that may allow the linking of genetic or medical information back to subjects.

To maximize confidentiality, all samples and the information associated with the samples will be coded to prevent the exposure of the participant's information and identity. In addition, sample information is stored in one secured database while genetic data is stored in an independent secured database.

9.9 Other Risks

Reviewing health-related information might be stressful or make the participant feel uncomfortable. Participants do not have to answer any questions they do not want to. In addition, there may be incidental medical findings as a result of the clinical examinations. Standard lab tests completed through MGH Core Lab will be placed in subjects' medical records but no additional research results will be placed in their medical records. Coded, de-identified data/samples may be provided to authorized federal data repositories for broad-sharing with approved researchers. As with all database systems, there is a slight risk that there could be a breach in the security of these data banks resulting in the access of information. Safeguards are in place to minimize privacy risks.

10 POTENTIAL BENEFITS

The aim of this trial is to further understand the effects of BCG on IIR and AD biofluid and MRI biomarkers and neurocognitive/behavioral functioning over one year. We do not know what the potential benefits may be to participants who choose to participate in this study. There may be no benefit at all. This trial is assessing multiple biomarkers in concert with clinical outcomes, which will provide a detailed understanding of the effect of BCG and provide a well-curated data set for the Alzheimer's research community to improve our understanding of the disease with an eye towards better treatments and prevention.

11 MONITORING AND QUALITY ASSURANCE

An Open Label Trial to Evaluate the Effects of BCG Immunization on Biomarkers of Inflammation/Immune Response and Alzheimer's Disease in Adults with Mild Cognitive Impairment and Mild-to-Moderate Dementia due to Alzheimer's Disease
Version Date#: October 13, 2022/Version 3.3

11.1 Independent Monitoring of Source Data

The PI will ultimately be responsible for the validity and integrity of the data collected at the MGH site, and for ensuring that the study is conducted in accordance with the IRB-approved protocol. After data is collected and recorded on forms, the study coordinator may input the data into the Partners approved StudyTRAX EDC within 7 days of the study visit. Entries will be reviewed for accuracy and completeness by a second study coordinator. Finally, the study team will conduct quarterly reviews to check that data in StudyTRAX accurately reflects the data collected on the original data capture forms and the PI will maintain oversight of this process. The research team (PI, Co-I, research coordinators) will subsequently meet to discuss the results of this review, as well as case report forms and source documentation.

All electronic documentation will be stored on password-protected devices. Paper forms will be stored in locked cabinets located in secured areas.

11.2 Safety Monitoring

The adverse event (AE) definitions and reporting procedures provided in this protocol comply with all applicable United States Food and Drug Administration (FDA) regulations and International Conference on Harmonization (ICH) guidelines. The PI will carefully monitor each subject throughout the study for possible adverse events. All AEs will be documented on CRFs designed specifically for this purpose. It will be important to report all AEs, whether serious or non-serious.

11.3 Adverse Event Reporting Guidelines

11.3.1 Adverse Event

An adverse event (AE) is any unfavorable and unintended sign (including a clinically significant abnormal laboratory finding, for example), symptom, or disease temporally associated with a study, use of a drug product or device, whether or not considered related to the drug product or device.

Examples of adverse events include: new conditions, worsening of pre-existing conditions, clinically significant abnormal physical examination signs (i.e. skin rash, peripheral edema, etc.), or clinically significant abnormal test results (i.e. lab values or vital signs), with the exception of outcome measure results, which are not being recorded as adverse events in this trial (they are being collected, but analyzed separately). The BCG vaccine causes a circular and contained inflammatory response with scab followed by scar formation. For this study, this expected BCG vaccine site reaction is not considered an adverse event. Stable chronic conditions (e.g. arthritis) that are present prior to the start of the study and do not worsen during the trial are NOT considered adverse events. Chronic conditions that occur more frequently (for intermittent conditions) or with greater severity are considered as worsened and therefore would be recorded as adverse events. Adverse events are generally detected in two ways:

- Clinical → symptoms reported by the subject or signs detected on examination.
- Ancillary Tests → abnormalities of vital signs, laboratory tests, and other diagnostic procedures (other than the outcome measures, the results of which are not being captured as AEs).

If discernible at the time of completing the AE log, a specific disease or syndrome rather than individual associated signs and symptoms should be identified by the PI and recorded on the AE log. However, if an observed or reported sign, symptom, or clinically significant laboratory anomaly is not considered by the PI to be a component of a specific disease or syndrome, then it should be recorded as a separate AE on the AE log. Clinically significant laboratory abnormalities, such as those that require intervention, are those that are identified as such by the PI.

Participants will be monitored for adverse events from the time they sign consent until completion of their participation in the study (defined as death, consent withdrawal, loss to follow up, early study termination for other reasons, or following completion of the entire study). An unexpected adverse event is any adverse event, the specificity or severity of which is not consistent with the current product insert.

The study procedures and the well-being of all participants will be monitored closely by the Principal Investigator, [name] MD, and the Co-Investigators [name] DNP, FNP-BC, and [name] M.D., Ph.D. Throughout the course of the study, constant feedback with the subject is maintained in order to assess comfort and safety and to minimize risks throughout the procedure. The above investigators will be responsible for determining if a subject should be removed from the study. Criteria for removal include the following: 1) if a subject is unwilling or unable to participate in study procedures 2) if the subject refuses to participate and consent, 3) if the subject acquires a medical condition that prohibits further participation, 4) if in the opinion of the MGH principal investigator, [name], it is decided that it is not in the subject's best interest to continue participation.

Unanticipated problems including adverse events will be reported to the PHRC as described in the PHRC policy on Unanticipated Problems Involving Risks to Subjects or Others including adverse events.

All data will be managed in compliance with applicable regulatory requirements. The study coordinator, under the supervision of the PI, will collect, transcribe, correct, and transmit the data onto source documents, Case Report Forms (CRFs), and/or other forms used to report, track, and record clinical research data.

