5.3 Discontinuation

5.3.1 Study Discontinuation

A study subject will be discontinued from participation in the study if:

1. Any clinical adverse event (AE), concurrent illness, or other medical condition or situation occurs such that continued participation in the study would not be in the best interest of the subject.
2. The subject meets any exclusion criteria (either newly developed or not previously recognized) and/or fails to continue to meet inclusion criteria which the study physician deems to be a risk to continued participation.

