5.3.2 Discontinuation of Study Intervention

Individual subjects will be allowed to continue in the study, but administration of the second immunization will be withheld if, after the first injection, any of the following criteria are met:

1. Any of the following serious adverse events attributable to BCG:
 - Life-threatening adverse event
 - Permanent or severe disability
 - Important BCG-specific medical events that do not result in death, are not life-threatening, and/or do not require hospitalization will be considered as serious if, based on appropriate medical judgment, they jeopardize the participant and would require medical or surgical intervention to prevent a serious adverse event.
2. Presentations of symptoms of disseminated BCG infection including persistent fevers, night sweats, weight loss. These symptoms may not occur within the timeline of the current study (they usually present 4 months to 2 years after vaccination), however should such symptoms occur prior to the second immunization, the study vaccine would be stopped.
3. The occurrence of any serious local skin reactions (\geq grade 3 ulceration, abscess formation, skin necrosis at the site of injection, or the development of suppurative lymphadenitis) as characterized by the standard FDA Toxicity grading scale (<https://www.fda.gov/regulatory-information/search-fda-guidance-documents/toxicity-grading-scale-healthy-adult-and-adolescent-volunteers-enrolled-preventive-vaccine-clinical>).

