5.4 Early Termination Visit (ET)

Subjects who decide to withdraw from the study at any point after receiving the initial BCG injection may be invited to come in for an Early Termination Visit.

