6.2.7 Visit 6 (Day 364 ± 28 days)

Subjects will be asked to return to MGH CNY for the final in-person visit at Day 364 (\pm 14 days) to assess study outcomes. This visit will take approximately four hours and will include:

- Vital signs
- Assess any changes to medical history, concomitant medications and/or adverse events
- Neurocognitive and behavioral assessments: FAQ, MoCA (version 8.1), CDR, RBANS (form a), NPI-Q, HADS, DCT Clock
- Blood draw for biomarkers
- Blood draw for LP safety
- Focused Exam: Fundoscopy
- Fasting CSF draw for biomarkers
- MRI (optional)
- Injection site monitoring

6.2.8 Phone Check 2 & 3 (Day 546 ± 28 days, Day 728 ± 28 days)

Subjects will be asked to complete a check-in phone call approximately 18 months and 2 years after the first injection to monitor safety. This will take about fifteen minutes and will:

- Collect any changes to medical history, concomitant medications, and/or adverse events

If the subject reports any new adverse events at the Phone Check that may require follow up, they will be referred to their primary care provider for further evaluation.

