8.2 Safety Endpoints

The primary safety endpoint will be the incidence of treatment emergent Grade II-IV adverse events.

Other safety endpoints are:

- Incidence and severity of treatment emergent adverse events (AEs)
- Clinical laboratory tests
- Vital signs
- Physical examinations
- Use of concomitant medications for treatment of AEs

All concomitant medications will be tabulated according to drug class and preferred term using the WHO dictionary. The safety data will be summarized by treatment group. Treatment AEs will be coded and graded using MedDRA grading criteria. The treatment groups will be compared with respect to occurrence of each adverse event and incidence of Grade II/IV adverse events. Withdrawal, abnormal laboratory tests, vital signs and use of concomitant medications used for treatment of AEs will be assessed to characterize the safety profile of BCG. Descriptive statistics denoting the changes from baseline to the final assessment visit with respect to key laboratory parameters and vital signs will also be provided.

Adverse events (AE) occurring after the start of study drug dosing at Baseline will be summarized descriptively. All AEs will be coded according to system organ class (SOC) and preferred term (PT) using a Medical Dictionary for Regulatory Activities (MedDRA) dictionary. Summary tables showing the number of subjects and percent within each category will be generated for each of the following types of adverse events and its relationship to study treatment (related to study treatment):

- All events
- Serious events
- Deaths
- Events leading to withdrawal
- Severe events

Treatment AEs will be coded and graded using MedDRA grading criteria. and compared with respect to occurrence of each adverse event and incidence of Grade II/IV adverse events. Total number of adverse events will be compared between groups using Fisher's exact test. Any treatment AE still present upon completion of treatment (including early discontinuation) should be monitored until resolution or until the AE is declared a chronic condition. AEs will be monitored until they become chronic or have completely resolved.

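### Adverse-event monitoring stops when a vaccinated participant is removed early, so new late-onset BCG events inside the protocol's own risk window are not asked about

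*Combined protocol and SAP*

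**What the plan says.** **When monitoring ends.** Section 11.3.1 runs AE monitoring from consent "until completion of their participation in the study (defined as death, consent withdrawal, loss to follow up, early study termination for other reasons", or completion of the whole study.

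**Who can be removed.** Section 5.3.1 opens "A study subject will be discontinued from participation in the study if". It then lists an AE, illness or other situation that makes continuing contrary to the participant's interest, and an eligibility failure that the study physician judges to be a risk. Section 11.3.1 adds further grounds, including "if a subject is unwilling or unable to participate in study procedures", a newly acquired medical condition, and the principal investigator's judgement.

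**What follows removal.** Under section 5.4, people who withdraw after the first injection "may be invited to come in for an Early Termination Visit". Section 6.2.9 lets them decline any part of that visit, or all of it. Section 8.2 continues follow-up of AEs still present at early discontinuation: "AEs will be monitored until they become chronic or have completely resolved". No section schedules a phone check after removal.

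**The risk period.** Section 9.1 names osteomyelitis as the most frequent disseminated BCG infection, "which usually occurs 4 months to 2 years after vaccination". Section 5.3.2 gives the same range for symptoms of disseminated infection, and remarks: "These symptoms may not occur within the timeline of the current study".

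**The safety calls.** Phone Check 1 is at Day 273 ± 5 (section 6.2.6). Phone Checks 2 and 3 are at Day 546 ± 28 and Day 728 ± 28, described in section 6.2.8 as "approximately 18 months and 2 years after the first injection to monitor safety". Dose 2 is given 28 to 42 days after dose 1 (section 6.2.3).

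**The concern.** Safety and tolerability is the first primary objective (section 3.2), and section 3.1 extends safety follow-up by phone into a second year. The most serious hazard that the protocol names is a late one. Yet a vaccinated participant whom the investigators remove leaves solicited AE follow-up on the day of removal, and the continued follow-up in section 8.2 does not reach an event that has not yet started.

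One route to removal shows why this matters. Starting immunosuppressive treatment is an exclusion criterion (section 4.1.2, item 7). If it arises later, section 5.3.1 item 2 can lead to discontinuation. Sections 7.7.2 and 9.1 identify immunocompromised people as those in whom the vaccine strain can become pathogenic. Such a person could leave the calls just as the reason to ask increases.

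Section 5.5 item 6 also stops the study on a single systemic BCG infection in a participant without underlying immunocompromise. That rule depends on the case becoming known.

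**Working it through.** **1. Reproducing the plan's calendar.** Weeks × 7: 4 → 28, 12 → 84, 26 → 182, 39 → 273, 52 → 364, 78 → 546, 104 → 728. All match the Schedule of Events, so the protocol's own two years is 104 weeks, or 728 days.

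**2. Is there any route by which a new event is solicited after removal?**

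- Section 11.3.1: monitoring has ended.
- Sections 5.4 and 6.2.9: one optional visit at the time of leaving, which cannot detect later onset.
- Section 8.2: only AEs still present.
- Section 5.3.2: keeps participants in the study when dose 2 is withheld, so they keep the calls. It does not apply to removal under 5.3.1 or 11.3.1, or to anyone removed after dose 2.
- Section 11.3.6: serious events are reported once an investigator is notified. This is passive.

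No route solicits new events.

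**3. Share of the dose-1 risk window covered, by day of removal.** Assumptions: 4 months = 122 days and 2 years = 730 calendar days, so the window is 730 − 122 = 608 days. Share = max(0, removal day − 122) / 608.

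| Removal day | Calculation | Share covered |
|---|---|---|
| 84 | before 122 | 0% |
| 122 | 0 / 608 | 0% |
| 182 | 60 / 608 | 10% |
| 273 | 151 / 608 | 25% |
| 364 | 242 / 608 | 40% |
| 546 | 424 / 608 | 70% |

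**4. Follow-up after dose 2 for those who complete every call.** Follow-up = call day − dose-2 day.

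| Call day | Dose-2 day | Follow-up (days) | Short of 728 | Short of 730 | Share of 4-month-to-2-year window |
|---|---|---|---|---|---|
| 700 | 42 | 658 | 70 | 72 | 536 / 608 = 88% |
| 728 | 42 | 686 | 42 | 44 | 564 / 608 = 93% |
| 728 | 28 | 700 | 28 | 30 | 578 / 608 = 95% |
| 756 | 28 | 728 | 0 | 2 | 606 / 608 = 99.7% |

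**5. How many cases are at stake.** Section 9.1 gives 0.01 to 43 osteomyelitis cases per million doses. With the maximum of 25 participants and two doses each, the upper end is 25 × 2 × 43 / 1,000,000 = 0.00215 expected cases.

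**The case against.** The strongest case against is that the gap is small and partly closed already. Much of it stands as a limit on the point.

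- **Vaccine problems after dose 1 do not by themselves mean removal.** Section 5.3.2 lets participants with BCG-attributable serious events, symptoms of disseminated infection or serious local reactions stay in the study with dose 2 withheld. A reader might infer that those removed are the ones most likely to have a vaccine problem. The documents do not support that.
- **Most of the quoted endpoints are proper.** Monitoring must end at death, and active contact ends when someone refuses it or cannot be found (section 5.3.4 already requires repeated attempts). The dispute is mainly about early termination on other grounds. Consent withdrawal is less clear: section 5.3.3 describes it in terms of future study procedures, and such a person might still accept a call.
- **Refusing a procedure is not the same as removal.** Section 6.2.11 treats procedures not performed as deviations, or not even that when illness is the reason. Unwillingness is a listed ground for removal in 11.3.1, but the investigators decide.
- **The number affected is unknown.** It is tempting to subtract the 12 expected completers (section 4.2) from the approximately 15 in section 8.1. Those figures have different bases, since 4.2 starts from up to 25 screened and enrolled, and the documents give no removal rate.
- **The expected case count is about 0.002 at most.** No late-event rate can be estimated here, so a claim of a biased rate would have little content. Nor is it right that the stop rule could never be triggered, because an unsolicited report could still reach the investigators.
- **The risk window is soft.** Both statements of it are qualified as the usual timing, which makes the dose-2 shortfall a small matter.

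None of this supplies a way to ask removed, vaccinated participants about new events.

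**Conclusion.** The point holds for vaccinated participants who are removed early. By the rule in section 11.3.1, they are not asked about new events during the period in which the protocol itself expects disseminated BCG infection to appear. Coverage of the dose-1 window is nil for removal by about Day 122 and partial after that, as tabulated. It would be too strong to say that the window is missed entirely for every early removal. Participants who stay in the study with dose 2 withheld are not affected.

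The timing of the last call is a minor, separate matter. With the call on Day 728, follow-up after dose 2 is 28 to 42 days short of 104 weeks. A reader might infer that nobody reaches two years after dose 2. On the protocol's 728-day convention that is wrong: dose 2 on Day 28 with a call on Day 756 reaches it exactly. Rollover participants receive dose 2 only approximately one month after dose 1 (section 6.1.1), and anyone given one dose has no dose-2 window.

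The remark in section 5.3.2 that symptoms may fall outside the study's timeline fits poorly with two years of follow-up. It is loose wording, not a contradiction.

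The gain is complete safety follow-up of everyone vaccinated, not a correction to an estimable event rate. No sample-size or power figure is affected. The percentages rest on 4 months = 122 days and 2 years = 730 days. The sponsor should make the change, though the trial does not fail without it.

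**What to change.** **Main change.** In sections 5.3.1, 5.4 and 11.3.1, separate stopping study procedures from stopping safety follow-up. Every participant who received at least one BCG dose keeps whichever of the existing Week 39, 78 and 104 phone checks remain, unless they decline contact or cannot be reached. AE monitoring for them ends after the last call.

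**Minor changes.** Reconcile the timing of Phone Check 3 (section 6.2.8 and the Schedule of Events) with a risk window that also runs from the second dose. Reconcile the timeline remark in section 5.3.2 with the two-year follow-up.

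**Cost.** A short amendment and matching consent wording, plus at most three calls of about 15 minutes per removed participant. No new procedures are needed. If the sponsor chose to count 104 weeks from dose 2, the last contact would fall on Day 728 + 28 = 756 to 728 + 42 = 770, against Day 728 now.
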